2.7.4 Supportive analyses

ORR, DOR, and PFS based on radiographic response by independent review assessment

The analyses of ORR, DOR, and PFS will be repeated based on radiographic response assessed by independent review by only incorporating the radiographic data which includes the lesion measurements from target lesions, non-target lesions, and new lesion per RANO. Clinical status data and corticosteroid use data will not be considered for the supportive analyses based on radiographic response. Waterfall plot will be presented for this analysis.

Waterfall graphs will be used to depict the anti-tumor activity for independent and investigator assessments.. These plots will display the best percentage change from baseline in the sum of the products of perpendicular diameters of all target lesions for each patient. Only patients with measurable disease at baseline will be included in the waterfall graphs. Special consideration is needed for assessments where the target lesion response is CR, PR or SD, but the appearance of a new lesion or a worsening of non-target lesions results in an overall lesion response of PD. A patient with only such assessments will be represented by a special symbol (e.g. \star) in the waterfall graph. Assessments with "unknown" target lesion response and assessments with unknown overall response will be denoted in the waterfall plots. Patients without any valid assessments will be completely excluded from the graphs.

The total number of patients displayed in the graph will be shown and this number will be used as the denominator for calculating the percentages of patients with tumor shrinkage and tumor growth. Bars will have different fill patterns for all possible values of overall response. Footnote will explain the reason for excluding some patients (due to absence of any valid assessment).

All possible assessment scenarios are described in Table 2-10.

Table 2-10	Inclusion/exclusion of assessments used in waterfall graph
------------	--

	Criteria for inclusio	on/exclusion		Possible sour contradictions	
case	Target response	Overall lesion response	Include in waterfall?	Non-target response	New lesion?
1	CR/PR/SD	PD	Yes as a bar	PD	any
2	CR/PR/SD	PD	Yes as a bar	any	Yes
3	UNK	UNK or PD	Yes as an x	any	any
4	CR/PR/SD	UNK	Yes as a bar	UNK	No

5	CR/PR/SD	CR/PR/SD	Yes as a bar	SD/IR	No
6	PD	PD	Yes as a bar	any	any

Additionally, swimmer plots of time to onset and DOR based on independent and investigator review will be created for the FAS.

Corticosteroids use

The drug name, dose, reason, dosing frequency per interval, and dose intensity will be listed. The dose intensity is calculated as the cumulative dose divided by the duration of exposure per interval. Any corticosteroids use starting and ending prior to the start of study treatment or starting more than 30 days after the last date of study treatment will be flagged in the listing.

New anticancer therapy sensitivity analysis for DOR and PFS

Response evaluations and events (i.e. RANO. documented disease progression or death) recorded after the initiation of new anti-neoplastic therapy will be included in sensitivity analyses of DOR and PFS, (i.e. the occurrence of new anti-neoplastic therapy will be ignored for the analyses). The sensitivity analyses will be performed based on both the investigator and independent review assessments using the FAS and using the same statistical methods for DOR and PFS described in Section 2.7.2. In the summary tables, this approach is referred as 'new anticancer therapy DOR sensitivity analysis' and 'new anticancer therapy PFS sensitivity analysis'.

2.8 Safety analyses

All safety analyses will be based on the safety set unless otherwise specified.

2.8.1 Adverse events (AEs)

AEs are coded using MedDRA terminology. The latest available MedDRA version at the time of the analyses should be used. The MedDRA version used for reporting will be specified in the CSR and as a footnote in the applicable tables/listings.

AEs will be assessed according to the Common Terminology Criteria for Adverse Events (CTCAE) version 4.03.

AE summaries will include all AEs occurring during on-treatment period. All AEs collected in the AE eCRF page will be listed along with the information collected on those AEs e.g. AE relationship to study drug, AE outcome etc. AEs with start date outside of on-treatment period will be flagged in the listings.

AEs will be summarized by number and percentage of patients having at least one AE, having at least one AE in each primary SOC and for each PT using MedDRA coding. A patient with multiple occurrences of an AE will be counted only once in the respective AE category. A patient with multiple CTCAE grades for the same PT will be summarized under the maximum CTCAE grade recorded for the event. AE with missing CTCAE grade will be included in the 'All grades' column of the summary tables.

In AE summaries, the primary SOC will be presented alphabetically and the PT will be sorted within primary SOC in descending frequency. The sort order for the PT will be based on their frequency.

The following AE summaries will be produced: overview of AEs and deaths (number and % of subjects who died, with any AE, any serious adverse event (SAE), any dose reductions/interruptions etc.), AEs by SOC and PT, summarized by relationship to study treatment (all AEs and AEs related to study treatment), seriousness (SAEs and non-SAEs), leading to treatment discontinuation, leading to dose interruption/adjustment, and leading to fatal outcome. In addition, a summary of serious and non-serious AEs with number of occurrences will be produced (an occurrence is defined as >1 day between start and prior end date of record of same PT) as per EudraCT requirements.

For legal requirements of clinicaltrials.gov and EudraCT, two required tables for on-treatment AEs which are not SAE's with an incidence greater than and equal to 5% and on-treatment SAE's and SAE's suspected to be related to study treatment will be provided by SOC and PT on the safety set population

2.8.1.1 Adverse events of special interest / grouping of AEs

All AE groupings for a clinical program are stored in the electronic Case Retrieval Strategy (eCRS) with clear versioning and reference to the MedDRA version used.

All adverse events of special interest (AESI) definitions or AE grouping need to be specified in the eCRS. If an eCRS update is necessary, the final version needs to be available before the final database lock. The eCRS version should be included in a footnote of the AESI tables.

Data analysis of AESIs

An AESI is a grouping of AEs that are of scientific and medical concern specific to dabrafenib and trametinib. These groupings are defined using MedDRA terms, standardized MedDRA queries (SMQ), high-level group terms, high-level terms) and PT. Customized Novartis MedDRA queries (NMQ) may also be used. An NMQ is a customized group of search terms which defines a medical concept for which there is no official SMQ available or the available SMQ does not completely fit the need. It may include a combination of single terms and/or an existing SMQ, narrow or broad. For each specified AESI, number and percentage of patients with at least one event of the AESI occurring during on-treatment period will be summarized. Any AESI categories with zero events will also be displayed in the summary tables.

AESI for dabrafenib and trametinib are:

- Skin related toxicities
- Ocular events
- Cardiac related events
- Hepatic disorders
- Pneumonitis/interstitial lung disease
- Bleeding events
- Hypertension

- Pyrexia
- Pre-Renal and intrinsic renal failure
- Uveitis
- New primary /secondary malignancy
- Hypersensitivity
- Hyperglycemia
- Venous thromboembolism
- Pancreatitis
- Neutropenia

Summaries of these AESIs will be provided by dabrafenib and trametinib, (specifying grade, SAE, relationship, leading to treatment discontinuation, leading to dose adjustment / interruption, fatal outcome, etc.). If sufficient number of events occurred, analysis of time to first occurrence will be applied.

A listing of all grouping levels down to the MedDRA preferred terms used to define each AESI will be generated.

2.8.2 Deaths

Separate summaries for on-treatment and all deaths including on-treatment and post-treatment deaths will be produced by SOC and PT.

All deaths will be listed for the Safety set, post-treatment deaths will be flagged. A separate listing of deaths prior to starting treatment will be provided for all screened patients.

2.8.3 Laboratory data

Data handling

Grade categorization of lab values will be assigned programmatically as per NCI CTCAE version 4.03. The calculation of laboratory CTC grades will be based on the observed laboratory values only, clinical assessments will not be taken into account. The criteria to assign CTC grades are given in Novartis internal criteria for CTC grading of laboratory parameters. The latest available version of the document based on the underlying CTCAE version 4.03 at the time of analysis will be used.

For laboratory tests where grades are not defined by CTCAE v4.03, results will be graded by the low/normal/high (or other project-specific ranges, if more suitable) classifications based on laboratory normal ranges.

A severity grade of 0 will be assigned for all non-missing lab values not graded as 1 or higher. Grade 5 is not applicable. For laboratory tests that are graded for both low and high values, summaries will be done separately and labeled by direction, e.g., sodium will be summarized as hyponatremia and hypernatremia.

Data analysis

On analyzing laboratory, data from all sources (central and local laboratories) will be combined. The summaries will include all assessments available for the lab parameter collected no later than 30 days after the last study treatment administration date (see Section 2.1.1).

The following summaries will be produced for hematology and biochemistry laboratory data (by laboratory parameter and treatment):

- Worst post-baseline CTC grade (regardless of the baseline status). Each subject will be counted only for the worst grade observed post-baseline.
- Shift tables using CTC grades to compare baseline to the worst on-treatment value
- For laboratory tests where CTC grades are not defined, shift tables using the low/normal/high/(low and high) classification to compare baseline to the worst on-treatment value.
- Trends of lab parameter values for serum creatinine over time (baseline and selected ontreatment time points) will be displayed via boxplots based on time windows for patients with values at baseline and 6 months or greater and corresponding tables displaying the statistics used for the box plots by the selected time points.

The following listings will be produced for the laboratory data:

- Listings of all laboratory data, with CTC grades and classification relative to the laboratory normal range. Lab data collected during the post-treatment period will be flagged.
- Listing of all CTC grade 3 or 4 laboratory toxicities

Liver function parameters

Liver function parameters of interest are total bilirubin (TBIL), alanine aminotransferase (ALT), aspartate aminotransferase (AST) and alkaline phosphatase (ALP). The number (%) of patients with worst post-baseline values as per Novartis Liver Toxicity guidelines will be summarized.

The following summaries will be produced:

- ALT or AST > 3xULN
- ALT or AST > 5xULN
- ALT or AST > 8xULN
- ALT or AST > 10xULN
- ALT or AST > 20xULN
- TBL > 2xULN
- TBL > 3xULN
- ALT or AST > 3xULN & TBL > 2xULN
- ALT or AST > 3xULN & TBL > 2xULN & ALP < 2xULN

Potential Hy's Law events are defined as those patients with occurrence of AST or ALT > 3xULN and TBL > 2xULN and missing ALP or ALP < 2xULN at any time during the ontreatment period. Note that the criteria relating to combined elevations of AST (or ALT) and TBL are based on the peak values at any post-baseline time for a subject.

For patients with abnormal ALT or AST baseline values, a clinically significant liver safety signal corresponding to Hy's law is defined by : [ALT or AST > 3xbaseline] OR [ALT or AST >8xULN], whichever is lower, combined with [TBIL >2xbaseline AND >2*ULN]A figure displaying time course of hepatic function tests (ALT, AST, TBL, ALP) in patients meeting Hy's criteria will be displayed in the Safety Set. Additonally, evaluation of drug-induced serious hepatotoxicity (eDISH) plots will be produced to display ALT and AST values by TBL values in units of ULN.

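### Potential Hy's law events can pair ALT/AST and bilirubin peaks from different times, and the ALP rule differs between the definition and the table row

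*SAP*

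**What the plan says.** The text is in section 2.8.3, Liver function parameters, of the HGG final SAP. The LGG final SAP and the two SAPs released in September 2021 carry the same rules.

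- Lead-in to the summaries: "The number (%) of patients with worst post-baseline values as per Novartis Liver Toxicity guidelines will be summarized".
- Two of the rows that follow: "ALT or AST > 3xULN & TBL > 2xULN" and "ALT or AST > 3xULN & TBL > 2xULN & ALP < 2xULN".
- Definition: "Potential Hy's Law events are defined as those patients with occurrence of AST or ALT > 3xULN" together with TBL > 2xULN "and missing ALP or ALP < 2xULN at any time during the ontreatment period".
- Timing note: the criteria for combined elevations of AST (or ALT) and "TBL are based on the peak values at any post-baseline time for a subject".
- Follow-up displays: a figure "displaying time course of hepatic function tests (ALT, AST, TBL, ALP) in patients meeting Hy's criteria", and eDISH plots. All laboratory data are also listed.

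No same-sample or window rule is given for any of the three tests. Missing ALP appears in the definition but not in the row. The figure does not say whether the definition or the row selects its patients.

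**The concern.** Hepatic disorders are an adverse event of special interest in both cohorts, and the combined ALT/AST and bilirubin count is the main laboratory liver signal. Two things weaken it.

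First, the count can include patients whose transaminase and bilirubin rises had nothing to do with each other in time. The chance of such a pairing grows with the number of samples. The HGG exposure categories run to 112 weeks and beyond. In the LGG cohort one arm has a fixed chemotherapy course while the other may be treated until progression.

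Second, the definition and the table row do not apply the same ALP condition, so two programmers following the text could report different numbers of patients.

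**Working it through.** The plan states no expected rate or count for these summaries, so there is no figure to reproduce. Two checks apply.

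**1. Four patient patterns under the plan's rules**

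| Pattern | Row without ALP | Definition | Row with ALP | Same-sample rule, missing ALP accepted |
|---|---|---|---|---|
| A. ALT > 3xULN at week 8, TBL > 2xULN at week 104, ALP normal | counted | counted | counted | not counted |
| B. ALT and TBL raised together, ALP never measured | counted | counted | not counted as written | counted |
| C. ALT and TBL raised together with normal ALP, ALP ≥ 2xULN at another visit | counted | counted | dropped if the highest ALP is used, kept if the concurrent one is | counted |
| D. ALT and TBL raised together with ALP ≥ 2xULN, ALP lower at another visit | counted | counted if any low ALP suffices, otherwise not | not counted if the highest or the concurrent ALP is used | not counted |

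A and B follow directly from the text. C and D depend on which ALP value is meant, which the plan leaves open.

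**2. How far the peak rule and a same-visit rule can diverge**

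Inputs from the documents: the chemistry schedule in Table 2-2 (weeks 2, 3, 4, 5 and 8, every 8 weeks to week 56, then every 16 weeks) gives 11 post-baseline visits by week 56, 14 by week 112 and 17 by week 160. The HGG cohort is about 40 patients. Assumptions, not in the documents: per-visit probabilities a (ALT/AST > 3xULN) and b (TBL > 2xULN), independent of each other and across visits.

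- Peak rule: P = [1 − (1 − a)^m] × [1 − (1 − b)^m]
- Same-visit rule: P = 1 − (1 − ab)^m

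For m = 14, a = 2%, b = 1%:

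- Peak: (1 − 0.98^14)(1 − 0.99^14) = 0.2464 × 0.1313 = 0.0323, and 40 × 0.0323 = 1.29 patients.
- Same visit: 1 − (1 − 0.0002)^14 = 0.0028, and 40 × 0.0028 = 0.11 patients.

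| a, b per visit | Peak rule, per 40 | Same visit, per 40 | Ratio |
|---|---|---|---|
| 1%, 0.5% | 0.36 | 0.03 | 12.7 |
| 2%, 1% | 1.29 | 0.11 | 11.6 |
| 5%, 2% | 5.05 | 0.56 | 9.1 |

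**LGG arms.** Chemotherapy lasts 12 + 8 × 6 = 60 weeks, which covers 11 scheduled visits. Targeted therapy can run longer; take week 160 (17 visits) as an example. With a = 2% and b = 1% in both arms:

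- Peak rule: 0.0209 at 11 visits and 0.0457 at 17, a ratio of 2.2.
- Same-visit rule: 0.0022 and 0.0034, a ratio of about 1.5.

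Longer observation raises any cumulative count. Under these assumptions the peak rule raises it further.

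**The case against.** The plan calls these events potential and states the peak basis openly. That is a sensitive screen, and the time-course figure, eDISH plots and listings let a reader see whether the peaks coincided. This stands, and it makes the point one of reporting rather than of a lost signal. It does not remove the need for a concurrent count, because the reported number is still the peak-based one and the figure inherits the unsettled selection rule.

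Four stronger readings are tempting and are not supported:

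- A reader might infer that the peak rule hides true cases. It cannot: a patient with concurrent elevations above the thresholds also has peaks above them. Only the row with ALP can lose such a patient, and the row without ALP keeps that patient.
- A reader might infer that the row uses the highest ALP, or that the definition's ALP condition screens out almost nothing. The lead-in speaks of worst values, but the timing note covers only AST/ALT and TBL. In the definition, the any-time phrase can govern the whole combination. Both readings are open.
- A reader might infer that the observation periods conflict, since the definition says on-treatment and the note says post-baseline. Section 2.8.3 limits laboratory summaries to 30 days after the last dose, which is where section 2.1.1 ends the on-treatment period.
- A reader might infer that long treatment has produced false cases. The documents show only that it can.

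Unequal exposure does affect every cumulative safety count in LGG. The point specific to this rule is the extra growth shown above.

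**Conclusion.** The point holds in limited form. Non-concurrent ALT/AST and bilirubin elevations can be counted as potential Hy's law events, more often with longer exposure. The definition and the ALP row also differ on missing ALP, and neither fixes which ALP value counts, so the row can omit patients whom the definition includes.

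The size is unknown from the documents. Over 112 weeks the illustration gives a peak-rule excess of about 0.3 to 4.5 patients per 40 (0.36 − 0.03 to 5.05 − 0.56). It rests entirely on assumed rates and on independence. Real liver injury raises both tests together and repeated values in one child are correlated, so the true ratio would probably be smaller. A rule with a time window would fall between the two columns. This is a cheap improvement to a reported safety count, not a failure to detect cases.

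**What to change.** In section 2.8.3 of both final SAPs:

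1. Keep the peak-based count and the eDISH plot, labelled as a screen that does not require concurrence.
2. Add a count of patients whose ALT/AST and TBL elevations fall within a stated window during the on-treatment period, with ALP taken from the same sample or the nearest one in that window. The sponsor should set and justify the window length before database lock.
3. State one rule for missing ALP and apply it to the definition, the ALP row and the selection of patients for the time-course figure.

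The cost is one extra table row and a date merge on laboratory data already held. The new count will not be directly comparable with the primary analysis; the retained peak count, worded as in the 2021 SAPs, preserves that comparison.

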2.8.4 Other safety data

2.8.4.1 ECG and cardiac imaging data

ECG Data handling

In case the study requires ECG replicates at any assessment, the average of the ECG parameters at that assessment should be used in the analyses.

ECG Data analysis

Standard 12-lead ECGs including PR, QRS, QT, QTcF, and HR intervals will be obtained local for each patient during the study. ECG data will be read and interpreted locally.

The number and percentage of patients with notable ECG values will be presented:

- QT, QTcF
 - New value of > 450 and ≤ 480 ms
 - New value of > 480 and ≤ 500 ms
 - New value of > 500 ms
 - Increase from Baseline of $> 30 \text{ ms to} \le 60 \text{ms}$
 - Increase from Baseline of > 60 ms
- PR
 - Increase from baseline >25% and to a value >200 ms
 - New value of > 200 ms
- QRS
 - Increase from baseline >25% and to a value > 120 ms
 - New values of QRS > 120 ms

The normal range for HR is displayed in Table 2-11 Recommendation for normal heart rate per age group and gender. The number and percentage of patients with notable values will be presented.

Age group	1-<3 years	3-<5 years	5-<8 years	8-<12 years	12-<16 years	16-<20 years	20-<30 years
HR (bpm) Boys	(95, 155)	(75, 125)	(60, 115)	(55, 100)	(50, 100)	(50, 105)	(45, 95)
HR (bpm) Girls	(95, 180)	(80, 125)	(70, 115)	(60, 110)	(50, 100)	(45, 105)	(50, 100)

Table 2-11Recommendation for normal heart rate per age group and gender

Age should be age at assessment. Data shown as upper limit of normal, lower limit of normal for HR= heart rate. Ref.: adapted from Rijnbeek et al. 2001 and Rijnbeek et al. 2014

The summaries will include all ECG assessments performed no later than 30 days after the last date of study drug. A listing of all ECG assessments will be produced and notable values will be flagged. A separate listing of only the patients with notable ECG values may also be produced. In the listings, the assessments collected during the post-treatment period will be flagged.

The denominator to calculate percentages for each category is the number of patients with both a baseline and a post-baseline evaluation. A newly occurring post-baseline ECG notable value is defined as a post-baseline value that meets the criterion post-baseline but did not meet the criterion at baseline.

For each ECG parameter, descriptive statistics at baseline, at each post-baseline time point and changes from baseline at each post-baseline time point will be summarized. Descriptive statistics at worst post-baseline and changes from baseline to worst post-baseline will also be summarized separately.

For each of the QTc and QT intervals, shift tables based on notable parameter categories (<450, 450-<481, 481-<501, ≥501 ms) at baseline and the worst post-baseline value observed.

Frequency counts and percentages of patients with newly occurring post-baseline qualitative ECG abnormalities (morphology) will be summarized. The denominator to calculate percentages is the number of patients with both a baseline and a post-baseline evaluation. A newly occurring post-baseline qualitative ECG abnormality is defined as a post-baseline abnormal finding which was not present at baseline.

Patients with notable ECG interval values and newly occurring qualitative ECG abnormalities will be listed and the corresponding notable values and abnormality findings will be included in the listings.

Unscheduled ECG measurements will not be used in computing the descriptive statistics for change from baseline at each post-baseline time point. However, they will be used in the analysis of notable ECG changes and the shift table analysis of notable QT parameters.

ECHO Data handling

ECHO data will be analyzed based on local reported results. The summaries will include all ECHO assessments performed no later than 30 days after the last date of study drug. All ECHO assessments will be listed, and those collected later than 30 days after study drug discontinuation will be flagged in the listing.

Novartis	Confidential	Page 37
SAP Final Analysis HGG		CDRB436G2201

The same modality (ECHO or MUGA) for determining cardiac scan data (e.g., left ventricular ejection fraction (LVEF)) should be used to follow a patient throughout the study. The absolute change from baseline values will not be calculated for any patients where the post-baseline value was determined by a cardiac scan modality that is different than the one used to determine baseline value.

ECHO Data analysis

Absolute change from baseline in LVEF will be summarized in the worst case post-baseline. Only the post-baseline assessments that used the same method (ECHO or MUGA) as the baseline assessments will be used to derive the change from baseline. The change from baseline will be categorized as follows:

- No change or any increase
- Any decrease:
 - \circ > 0 <10% Decrease
 - 10 <20% Decrease
 - $\circ \geq 20\%$ Decrease
- $\geq 10\%$ decrease and $\geq LLN$
- $\geq 10\%$ decrease and < LLN
- $\geq 20\%$ decrease and $\geq LLN$
- $\geq 20\%$ decrease and < LLN

ECHO assessments of LVEF will be listed for each patient including absolute change from baseline at each assessed time interval. The values of potential clinical importance will also be flagged.

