Week 4 Day 1	Study Day 22	Study Days 20 – 24
Week 5 Day 1	Study Day 29	Study Days 27 – 31
Week 8 Day 1	Study Day 50	Study Days 43 – 57
Every 8 weeks thereafter		
Week y=8+8*k	Study Day (8+8*k-1)*7+1	Study Day
(with k = 1, 2,, 6)		(8+8*k-1)*7+1-7 to
		(8+8*k-1)*7+1+7
Every 16 weeks thereafter		
Week y=56+16*k	Study Day (56+16*k-1)*7+1	Study Day
(with k = 1, 2, …)		(56+16*k-1)*7+1-7 to
		(56+16*k-1)*7+1+7
End of treatment (EoT)		
EoT	Within 30 days after last dose	Earliest data available on or

Time Window	Planned Visit Timing	Time Window Definition
		after EoT date up to and including 30 days after EoT
Post treatment ^b		
Post treatment follow-up 1	Post treatment study day 16*7	Post treatment Study Days 16*7 - 14 to 16*7 + 14
Post treatment follow-up k (with k = 2, 3,)	Post treatment study day 16*k*7 30	Post treatment study days 16*k*7 - 14 to 16*k*7 + 14

^aStudy Day 1 = start date of study treatment

^bPost treatment study day 1=end of treatment date + 1 day

Table 2-3 Time windows for ECG/Visual Acuity

Time Window	Planned Visit Timing	Time Window Definition
On treatment		
Baseline (Week 1 Day 1)	On or before Study Day 1 ^a	≤ Study Day 1
Week 5 Day 1	Study Day 29	Study Days 27 – 31
Week 16 Day 1	Study Day 106	Study Days 99 – 113
Week 32 Day 1	Study Day 218	Study Days 211 – 225
Week 48 Day 1	Study Day 330	Study Days 323 – 337
Week 72 Day 1	Study Day 498	Study Days 491 – 505
Every 16 weeks thereafter		
Week y=16+16*k	Study Day (16+16*k-1)*7+1	Study Day
(with k = 1, 2,)		(16+16*k-1)*7+1-7 to
		(16+16*k-1)*7+1+7
End of treatment (EoT)		
EoT	Within 30 days after last dose	Earliest data available on or
		after EoT date up to and
		including 30 days after EoT

For all analyses regarding abnormal assessments or analyses based on worst or best postbaseline value (laboratory, ECGs, vital signs, Karnofsky/Lansky performance status, echocardiogram (ECHO), ophthalmologic exam, dermatologic exam, etc.), all post-baseline values will be included (scheduled, unscheduled, repeat).

Last contact date

The last contact date will be derived for patients not known to have died at the analysis cut-off using the last complete date among the sources specified in Table 2-4.

Table 2-4	Last contact date	data sources
	Luot contact auto	

Source data	Conditions
Date of Randomization	No Condition
Last contact date/last date patient was known to be alive from Survival Follow-up page	Patient status is reported to be alive, lost to follow-up or unknown.

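### The definition of a new QT/QTcF value, applied to bounded bands, counts a fall from a higher baseline band as newly notable; the shift table also cuts at slightly different limits

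*SAP*

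**What the plan says.** Section 2.8.4.1 (ECG Data analysis) of the HGG final SAP plans a table of notable values: "The number and percentage of patients with notable ECG values will be presented". For QT and QTcF it has three rows on the absolute value:

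- "New value of > 450 and ≤ 480 ms"
- "New value of > 480 and ≤ 500 ms"
- "New value of > 500 ms"

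Two further rows cover increases from baseline (more than 30 up to 60 ms, and more than 60 ms).

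A newly occurring notable value is "a post-baseline value that meets the criterion post-baseline but did not meet the criterion at baseline". The denominator is stated: "The denominator to calculate percentages for each category is the number of patients with both a baseline and a post-baseline evaluation". For analyses of abnormal, worst or best values, section 2.1.1 says that "all post-baseline values will be included (scheduled, unscheduled, repeat").

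The same section then plans, for QT and QTc, "shift tables based on notable parameter categories (<450, 450-<481, 481-<501, ≥501 ms"), crossing the baseline category with the worst post-baseline value.

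Section 2.8.4.1 of the LGG final SAP has the same bands, definition and shift categories, with the notable-value rows shown by treatment group. The 2021 SAPs (HGG Amendment 2 and LGG Amendment 1) carry the same text.

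**The concern.** The definition of new asks only whether the criterion was unmet at baseline. For a criterion open at the top, such as >500 ms, unmet at baseline means that the baseline was lower, so meeting it later is a rise. For a band closed at both ends, unmet at baseline can also mean that the baseline was above the band. The rule has no condition on direction, so a patient whose interval shortens into the band meets it.

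The two lower rows would then mix new prolongation with improvement, and two outputs from one section would describe the same patient in opposite ways. The different limits in the shift table are a second, smaller source of disagreement between those outputs.

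**Working it through.** No power or sample-size figure is involved, so the check is to apply the rules of section 2.8.4.1 literally to example series.

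**Inputs.** Bands: B1 = >450 to ≤480, B2 = >480 to ≤500, B3 = >500 ms. New in a band = some post-baseline value lies in the band and the baseline value does not. Shift categories: S0 = <450, S1 = 450 to <481, S2 = 481 to <501, S3 = ≥501 ms, using the worst post-baseline value.

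**Step 1: direction.**

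| Baseline (ms) | Post-baseline (ms) | New under the stated definition | Shift table |
|---|---|---|---|
| 440 | 460 | B1 | S0 to S1, worse |
| 490 | 430 | none | S2 to S0, improved |
| 490 | 470 | B1 | S2 to S1, improved |
| 510 | 470 | B1 | S3 to S1, improved |
| 510 | 490 | B2 | S3 to S2, improved |

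The first two rows behave as intended. In the last three the interval fell, yet the patient qualifies as new. For 490 to 470: 470 satisfies >450 and ≤480, and 490 does not because it exceeds 480.

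The fault is confined to B1 and B2. B3 is open at the top, as are the PR (>200 ms) and QRS (>120 ms) criteria, and for these the definition works.

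**Step 2: limits.** For whole milliseconds, >480 is the same as ≥481 and >500 the same as ≥501, so those two cuts agree. But >450 is the same as ≥451, whereas the shift table cuts at ≥450. Matching B1, B2 and B3 to S1, S2 and S3 over the integers 300 to 699, the only mismatch is 450 ms: not notable in one table, S1 in the other.

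For fractional values there are two more gaps:

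- 480.5 ms is B2 (>480) but S1 (<481).
- 500.5 ms is B3 (>500) but S2 (<501).

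Section 2.8.4.1 has replicate ECGs averaged if the study requires replicates, which is one way that fractions could arise.

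**Step 3: the corrected rules on the same series.**

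- *Worst post-baseline band higher than baseline band:* 490 to 470, 510 to 470 and 510 to 490 give no new value; 440 to 460 is new in B1; 440 to 460, 490, 510 is new once, in B3.
- *One-sided thresholds >450, >480, >500, with baseline not above the threshold:* 490 to 470 gives none, and 510 to 470, 490 gives none; 440 to 460, 490, 510 is new at all three, which are then openly cumulative.

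**The case against.** The strongest reply is that the shift table already answers the safety question. It places each patient once by worst post-baseline value and shows direction, so the 490 to 470 patient sits in an improvement cell. The section also summarises change from baseline to worst value, has separate increase-from-baseline rows, and lists all ECGs with notable values flagged. This stands. A reader might infer that the number of children with new prolongation cannot be recovered from the planned outputs; the shift table shows that it can. What remains is that the notable-value rows, read on their own, include falls.

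Three further inferences go beyond the document:

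- *That one patient is counted in several bands.* Values of 460, 490 and 510 ms would meet all three criteria if each value were scored. But section 2.1.1 says which assessments are eligible, not that each one scores its own row. Laboratory grades in section 2.8.3 are expressly counted once at the worst grade, and for pulse in section 2.8.4.2 counting in several categories is expressly allowed. For QT neither is stated. Even if patients did appear in more than one row, percentages are given per category and the rows are never summed, so this is not an error.
- *That the limits conflict broadly.* For whole milliseconds they differ only at 450 ms. The other gaps need fractional values, and the averaging of replicates is conditional.
- *That the denominator is wrong.* It is stated explicitly, and nothing shows an error in it.

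**Conclusion.** Wrong as written, and minor. Under the stated definition a fall from a higher baseline band into >450 to ≤480 or >480 to ≤500 ms counts as a newly notable QT/QTcF value, in contradiction to the shift table for the same patient. The shift limits also disagree with the notable-value rows at exactly 450 ms, and would disagree for fractional values above 480 and below 481 ms, or above 500 and below 501 ms.

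The size is unknown. A false new case needs a baseline above 480 ms followed by a value in a lower notable band, and the SAPs give no baseline QT distribution. No percentage can responsibly be attached. Only descriptive safety tables are touched; no efficacy result depends on them.

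The conclusion assumes that the definition is programmed literally. A programmer might supply the missing direction condition unprompted, but the text does not ask for it.

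**What to change.** In section 2.8.4.1 of both final SAPs:

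1. For the QT/QTcF rows, count a value as new only if the patient's worst post-baseline band is higher than the baseline band. This also settles that a patient appears in one band only. Alternatively, replace the bands with one-sided thresholds >450, >480 and >500 ms, new when the worst post-baseline value exceeds the threshold and the baseline does not, and label the rows as cumulative.
2. Set the shift categories to ≤450, >450 to ≤480, >480 to ≤500 and >500 ms, so that both tables use the same limits for whole and fractional values.
3. Leave the denominator as stated.

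The cost is a few lines of SAP text and a small programming change, with no new data. Because the 2021 SAPs, which cover the primary analysis, carry the same wording, a footnote should say that the definition differs from any notable-value rows already produced under it.
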